7.5.2.3 Recommendations for Treatment of Rash/Skin toxicity

Early identification and intervention is critical for the optimal management of rash. Preliminary clinical evidence suggests that antihistaminergic drugs may ameliorate occurance/severity of rash. Therefore, patients who develop Grade 1 or 2 changes in their skin condition should be treated with the Investigator's choice of antihistaminergic drugs, over the counter moisturizing cream or ointment, local antihistamines and/or topical or systemic steroids. If bacterial infection is suspected, local and/or systemic antibiotics may be added.

For Grade 3 rash, topical and/or systemic steroids with or without topical and/or systemic antibiotics (to be considered if bacterial infection is suspected) are indicated, together with dose modifications as described in *Section 7.5.1*; short courses (\leq 14 days) of corticosteroid treatment at doses that do not exceed 100 mg per day of prednisone or equivalent may be given.

Some example treatments are listed below:

- Topical steroids: triamcinolone acetonide 0.025%; desonide 0.05%; fluticasone proprionate 0.05%, aclometasone 0.05%
- Topical antipruritics: pramoxine 1%; doxepin 5% cream
- Oral antihistamines: loratidine, cetirizine, fexofenadine; diphenhydramine 25-50 mg every 8h; hydroxyzine 25 mg every 8h
- Topical antibiotics: clindamycin 1-2%; erythromycin 1-2%; metronidazole 1%; silver sulphadiazine1%
- Oral antibiotics: doxycycline 100 mg BD; minocycline 100 mg BD; oxytetracycline 500 mg

In the event of Steven-Johnson syndrome, an immune-complex-mediated hypersensitivity that typically involves the skin and mucous membranes (Grade 3-4 Skin Sloughing), patients should permanently discontinue rituximab and AZD2014 treatment.

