4.2 Exclusion Criteria

Patients must not enter the study if any of the following exclusion criteria are fulfilled:

 Prior chemotherapy, biological therapy, radiation therapy, androgens, thalidomide, immunotherapy, other anticancer agents, and any investigational agents within 21days of registration (not including palliative radiotherapy at focal sites to non-target lesions). Corticosteroids are permitted during screening but should be weaned down to a maximum dose of prednisolone 10mg daily (or equivalent) by day 1 of cycle 1.

- With the exception of alopecia, any unresolved toxicities from prior chemotherapy should be no greater than CTCAE (Version 4.0) Grade 2 at the time of registration.

- 2. Major surgery within 4 weeks prior to entry to the study (excluding placement of vascular access), or minor surgery within 2 weeks of entry into the study.
- 3. Exposure to potent or moderate inhibitors or inducers of CYP3A4/5, Pgp (MDR1) and BCRP if taken within the stated washout periods before the first dose of study treatment. See Appendix 2.
- 4. Exposure to sensitive or narrow therapeutic range substrates of the drug transporters Pgp (MDR1), BCRP, MATE 1, MATE 2K, OATP1B1 and OATP1B3, within the appropriate wash-out period (a minimum of 5 x the reported terminal elimination half-life of each drug) before the first dose of study treatment. See table in appendix 3.
- 5. Previous treatment with any first generation mTORC1 inhibitors (rapamycin, sirolimus, temsirolimus, everolimus) or any dual mTORC1/2 inhibitors (e.g. AZD2014, AZD8055).
- 6. Patients who have experienced intolerable AEs prejudged by the treating Investigator due to other mTORC1 or mTORC1/2 inhibitors, PI3 kinase inhibitors, or AKT inhibitors.
- 7. Patients with proven central nervous system (CNS) involvement.
- 8. As judged by the Investigator, any evidence of severe or uncontrolled systemic diseases (e.g., severe hepatic impairment, interstitial lung disease (e.g.bilateral, diffuse, parenchymal lung disease), uncontrolled chronic renal diseases (e.g. glomerulonephritis, nephritic syndrome, Fanconi Syndrome or Renal tubular acidosis) or current unstable or uncompensated respiratory or cardiac conditions, or uncontrolled hypertension, active bleeding diatheses or active infection. Screening for chronic conditions is not required.
- 9. Patients who have experienced any of the following procedures or conditions currently or in the preceding 12 months:

- coronary artery bypass graft

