7.2 Treatment Schedule

AZD2014 is to be administered twice daily orally on an intermittent schedule at a dose of 125mg. Two consecutive days of treatment will be followed by 5 days with no treatment each week. Treatment would therefore be on days 1, 2, 8, 9, 15, 16, 22 and 23 of each cycle of 28 days. Treatment days should be two consecutive days and should be the same days each week, for example if treatment was started on a Monday in the first week further treatments would be expected to continue to be on Mondays and Tuesdays each week. Treatment will continue until progression or withdrawal due to toxicity or due to patient choice.

For the second, combination, stage of the trial, rituximab 375mg/m² will also be administered intravenously in the standard fashion as per local protocol on day 1 of the 28 day cycle for a total of 6 cycles. Pre-medication with antihistamines (e.g.Piriton), hydrocortisone and paracetamol is permissive as per local protocols for use of rituximab in the 6 patient combination stage.

Where possible all doses of AZD2014 should be taken at approximately the same times each day. AZD 2014 doses can be taken with or without food. Twice daily doses should be taken approximately 12 hours apart. If vomiting occurs within 30 minutes after AZD2014 dosing, or if the tablet(s) can be identified in the vomit content, the patient can re-take new tablet(s).

If a patient misses a dose and remembers within 2 hours, they should take the dose straight away and continue to take the rest of their medication as planned. If a dose is missed and the patient remembers after 2 hours or longer, they should take the next dose when it is due

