7.5.1 General dose modifications for toxicities

Dose reduction and discontinuation guidelines for haematologic and non-haematologic toxicities due to AZD2014 are shown in Table 2 and 3. Dose re-escalation is not permitted.

Table 2.	Dose modifications and discontinuation criteria for non-haematologic toxicities*

NCI CTCAE Toxicity Grade	Action
Grade 1, or 2	None
Grade 3 or 4 and/or clinically significant	
Expected manageable/reversible with dose reduction	Hold study drug until meets one of the criteria below:
Toxicity remains (despite dose interruption) grade 3 or 4 or is clinically significant > 14 days	Discontinue study drug
Toxicity lasts 14 days or less and resolves to grade 2 or less or is no longer clinically significant	Reduce dose level per Table 1 and restart once toxicity has resolved to grade 2 or less or is no longer clinically significant
Grade 3 or 4 and/or clinically significant	
Not expected to be manageable/reversible with dose reduction	Discontinue study drug
Recurrence of Grade 3	Reduce one more dose level is available (see table 1), or if not discontinue study drug. NB note option of continuous dosing schedule as mentioned in 7.5

 Table 2.
 Dose modifications and discontinuation criteria for non-haematologic toxicities*

NCI CTCAE Toxicity Grade Action	
Recurrence of Grade 3 cardiac event ^a	Discontinue study drug
Recurrence of Grade 4	Discontinue study drug

* If the below specific recommendations for stomatitis/oral mucositis, hyperglycaemia, ILD/pneumonitis, ECG-changes and rash disagree with table 2 please follow the below not recommendations not table 2.

	Table 3.	Dose modifications and discontinuation criteria for haematological toxicitie
--	----------	--

NCI CTCAE toxicity grade	Action
Thrombocytopenia	
Grade 1, 2 or 3 (without bleeding)	None
Grade 3 (with bleeding) or grade 4	Hold study drug until it meets one of the criteria below:
Toxicity remains (despite dose interruption) grade 3 (with on-going bleeding episodes) or 4 > 14 days	Discontinue study drug
Toxicity lasts 14 days or less and resolves to grade 2 or less	Reduce dose level per table 1 and restart once toxicity has resolved to grade 2 or less
Neutropenia (NB GCSF is permitted as per local p	olicy)
Grade 1, 2 or 3	None
Grade 4	Hold study drug until it meets one of the criteria below:
Toxicity remains (despite dose interruption and GCSF) grade 4 > 14 days	Discontinue study drug

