7.8 Concomitant Medication

7.8.1 Concomitant treatment with CYP inhibitors, inducers and substrates

If a patient requires short-term administration of a restricted CYP3A4/5, Pgp or BCRP **inhibitor** AZD2014 treatment must be withheld for three days prior to administration and not restarted until the concomitant therapy has been discontinued for the appropriate time period described in Appendix 2.

If a patient requires short-term administration of a restricted CYP3A4/5, Pgp (MDR1) or BCRP isoenzyme **inducer** this should be clearly documented in the Case Report Form (CRF) and may then be permitted, but the Investigator will be informed that this could lead to lower levels of study drug and a potential reduction in clinical efficacy.

If a patient requires short term administration of restricted **substrates** of OATP1B1, OATP1B3, MATE1 or MATE2K AZD2014 treatment must be withheld for 3 days prior to the first administration and not restarted until the concomitant therapy has been discontinued for the appropriate time period *described in Appendix 3*.

Information on all concomitant treatments given during the study with reasons for the treatment should be recorded in the CRF. If medically feasible, patients taking regular medication other than those excluded from this study should be maintained on it throughout the study period.

The lists of CYP inhibitors, inducers and substrates are not exhaustive and the absence of a drug from these lists does not imply that its combination with AZD2014 is safe.

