APPENDIX 2 – POTENT OR MODERATE INHIBITORS OR INDUCERS OF CYP3A4/5, PGP (MDR1) AND BCRP

Cytochrome P450 and transporter inhibitor/inducer restrictions		
CYP/ Transporter Category	Drugs	Minimum drug wash-out period
CYP3A4/5Strong Competitive inhibitors	grapefruit juice, indinavir, itraconazole, ketoconazole, nefazodone, nelfinavir, saquinovir, telithromycin and troleandomycin and voriconazole	1 week 2 weeks
	idelalisib	
CYP3A4/5 Strong Time dependent inhibitors	bocepravir, clarithromycin, cobicistat, danoprevir, elvitegravir, LCL161, lopinavir, mibefradil*, posaconazole, ritonavir, telaprevir and tipranivir	2 weeks
CYP3A4/5 Strong inhibitors (classification unknown)	conivaptan	1 week
CYP3A4/5 Moderate Competitive inhibitors	amprenavir, aprepitant, atazanavir, cimetidine, cyclosporine, fluconazole, imatinib and netupitant	1 week
CYP3A4/5 Moderate Time dependent inhibitors	ACT-178882, casopitant, crizotinib, darunavir, diltiazem erythromycin, ledipasvir, lomitapide, tofisopam and verapamil	2 weeks
	FK1706	half-life not found
CYP3A4/5 Moderate inhibitors (classification not known)	ciprofloxacin and dronedarone	1 week
	schisandra sphenanthera	half-life not found
CYP3A4/5 Strong inducers	carbamazepine, phenytoin, rifabutin, rifampicin and St. John's Wort	3 weeks
	enzalutamide and phenobarbital	5 weeks
	mitotane avasimibe	114 weeks half-life not found

Cytochrome P450 and transporter inhibitor/inducer restrictions		
CYP/ Transporter Category	Drugs	Minimum drug wash-out period
CYP3A4/5 Moderate inducers	bosentan, genistein, lersivirine, lopinavir, modafinil, nafcillin, ritonavir, semagacestat, , thioridazine and tipranavir	1 week
	etravirine efavirenz	2 weeks 3 weeks
Pgp (MDR1) inhibitors	talviraline dronedarone, erythromycin, indinavir, itraconazole,	half-life not found 1 week
	ketoconazole, lapatinib, lopinavir, ritonavir, quinidine and verapamil vorapaxer	10 weeks
	valspodar (PSC 833)	half-life not found
Pgp (MDR1) inducers	carbamazepine and rifampin	3 weeks
BCRP inhibitors	atazanavir, cyclosporine, lopinavir, ritonavir and tipranavir	1 week

APPENDIX 3 - SENSITIVE OR NARROW THERAPEUTIC RANGE IN VIVO SUBSTRATES OF THE DRUG TRANSPORTERSMATE, OATP & OCT

Transporter Substrate Restrictions

Transporters	Substrates
OATP (1B1 or 3)	bosentan, fexofenadine, glyburide, pitavastatin, pravastatin, repaglinide , rosuvastatin
MATE (1 or 2K)	cisplatin

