Substrates in bold type have a narrow therapeutic index. Reference: Expert Opin. Drug Metab. Toxicol. (2013) 9(6):737-751. Washout periods should be 5 x reported terminal half-lives.

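### The rash guidance names fexofenadine without caveat, although Appendix 3 restricts it and Section 7.8.1 requires AZD2014 to be withheld around it

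*Protocol*

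**What the plan says.** - **Section 7.5.2.3 (rash).** Grade 1 or 2 skin changes are to be treated with an antihistamine of the investigator's choice, among other measures. The example list begins "Oral antihistamines: loratidine, cetirizine, fexofenadine" and continues with diphenhydramine and hydroxyzine, five agents in all. Fexofenadine carries no warning and no pointer to another section. The section opens: "Early identification and intervention is critical for the optimal management of rash".
- **Appendix 3.** The OATP (1B1 or 3) row of the restricted-substrate table reads "bosentan, fexofenadine, glyburide, pitavastatin, pravastatin" and goes on to two further drugs. The note beneath adds: "Washout periods should be 5 x reported terminal half-lives".
- **Section 7.8.1.** For short-term use of a restricted OATP1B1, OATP1B3 or MATE substrate, "AZD2014 treatment must be withheld for 3 days prior to the first administration and not restarted until the concomitant therapy has been discontinued" for the Appendix 3 period.
- **Section 4.2, exclusion criterion 4.** It bars patients with "Exposure to sensitive or narrow therapeutic range substrates of the drug transporters Pgp (MDR1), BCRP, MATE 1, MATE 2K, OATP1B1 and OATP1B3" within five half-lives before the first dose, and points to Appendix 3. The synopsis version also covers OATP1B1 and OATP1B3.
- **Section 7.5.1, Table 2.** The action for Grade 1 or 2 non-haematologic toxicity is none. The footnote begins "If the below specific recommendations for stomatitis/oral mucositis, hyperglycaemia, ILD/pneumonitis, ECG-changes and rash disagree with table 2" and tells sites to follow the specific recommendations in that case.

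**The concern.** The toxicity guidance that a site opens when a patient develops a rash offers a drug that the concomitant-medication rule restricts, and gives no prompt to check that rule. A clinician who follows Section 7.5.2.3 alone would give fexofenadine alongside AZD2014 and breach a mandatory interaction safeguard. A clinician who follows both sections would have to stop AZD2014 three days before treating the rash, which defeats the early intervention that the section calls for. That clinician might also have to forgo active treatment for a low-grade event.

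The same drug, taken within its washout before the first dose, would have kept the patient out of the trial. At stake are patient safety and consistent conduct across sites. No sample-size or error-rate figure is in question.

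**Working it through.** There is no plan figure to reproduce. The check is a cross-reading of the sections, followed by whether the weekly off-days can absorb the required hold.

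**Cross-reading**

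1. Is fexofenadine restricted? Yes, it is named in Appendix 3. Bold type there marks a narrow therapeutic index, but the appendix title and exclusion criterion 4 cover sensitive or narrow-range substrates, so every listed drug is included.
2. Is it exempted anywhere? No. Section 7.8.2 leaves other medication that is needed for safety and well-being to the investigator's discretion. It does not mention fexofenadine or lift the specific rule in Section 7.8.1.
3. Does the rash section take precedence? Only over Table 2. The footnote says nothing about Section 7.8.1.
4. Are the other four oral antihistamines restricted? None appears in Appendix 2 or Appendix 3.

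**Inputs for the timing check**

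- AZD2014 is taken on two consecutive days each week (Section 7.2), and "Twice daily doses should be taken approximately 12 hours apart". Doses therefore fall at t = 0, 12, 24 and 36 h, and the next block starts at t = 168 h.
- Pre-hold: 3 days = 72 h (Section 7.8.1).
- Washout: 5 × half-life (Appendix 3).
- Assumed, because the documents do not state them: fexofenadine once daily; a 7-day course for the illustration; a half-life of 10–20 h.

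**Room in the off-period**

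- Gap between blocks: 168 − 36 = 132 h.
- Left after the pre-hold: 132 − 72 = 60 h.
- Share of the week that is at least 72 h after the last AZD2014 dose: 60/168 = 35.7%. At other times, starting fexofenadine means waiting up to 3 days.

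**Longest half-life that fits without a missed dose**

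A course of n daily doses spans 24(n − 1) h, so the half-life must be at most (60 − 24(n − 1))/5.

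| Daily doses n | Span (h) | Maximum half-life (h) |
|---|---|---|
| 1 | 0 | 60/5 = 12.0 |
| 2 | 24 | 36/5 = 7.2 |
| 3 | 48 | 12/5 = 2.4 |
| 4 | 72 | none (72 > 60) |

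Four or more daily doses cannot fit even with zero washout. Given once-daily dosing, that result does not depend on the half-life.

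**Seven daily doses, best timing**

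- Span: 24 × 6 = 144 h. Washout at 10–20 h: 50–100 h.
- Interval free of AZD2014: 72 + 144 + 50 = 266 h (11.1 days) to 72 + 144 + 100 = 316 h (13.2 days). This includes the 132 h that are scheduled off anyway.
- It runs from t = 36 h to t = 302–352 h.
- Missed AZD2014 doses: those at 168, 180, 192 and 204 h throughout the range, plus those at 336 and 348 h when the half-life is 20 h. That is 4–6 doses, or 4 × 125 = 500 mg to 6 × 125 = 750 mg.

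**The case against.** The strongest reply is that this is a missing cross-reference and not a contradiction. Section 7.5.2.3 only gives examples, the choice is the investigator's, and Section 7.8.1 permits a restricted substrate provided AZD2014 is held. Both sections can be obeyed together. That is logically correct. It does not rescue the text, because the rash section never mentions the hold, and obeying both means a delay of up to 3 days and, for an ordinary daily course, missed treatment.

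Other points on that side, and what stands of each:

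- **Entry criterion.** A stricter rule at entry than on treatment is a legitimate design, so criterion 4 is context and not a second inconsistency. This stands.
- **Table 2.** Its entry of no action concerns the toxicity itself, not holds that another drug requires. This also stands: there is no formal clash with Table 2. The practical result is still that AZD2014 is interrupted for an event that would not otherwise call for it.
- **Illustration.** The half-life, the once-daily frequency and the 7-day course are assumptions, and the 11.1–13.2 days include the scheduled rest. The real loss is the 4–6 missed doses.
- **Other listed drugs.** Section 7.5.2.3 also names topical erythromycin, and Appendix 2 lists erythromycin without a route. Section 7.5.2.1 allows an unspecified H2 blocker, and Appendix 2 lists cimetidine. These are weaker cases, since topical exposure may be negligible and other H2 blockers can be chosen. They leave the fexofenadine point intact.
- **Weight.** Section 1.2.3.2 reports no rash so far on intermittent schedules, and four other oral antihistamines are named. The problem may almost never arise. This stands and limits the importance of the point.

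**Conclusion.** The concern holds. Section 7.5.2.3 recommends, without qualification, a drug that Appendix 3 restricts and around which Section 7.8.1 requires AZD2014 to be withheld. That follows from the protocol's text alone.

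For once-daily use, a course of four days or more cannot be reconciled with Section 7.8.1 without missed AZD2014 doses, whatever the half-life. The figure of 4–6 missed doses (one weekly block, up to one and a half) also rests on the assumed 7-day course, the assumed 10–20 h half-life and best timing.

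It should be corrected, but the weight is minor. A site can avoid the problem by choosing another listed antihistamine, how often it would arise may be near zero, no stated power or error rate is wrong, and no effect on the tolerability endpoint is claimed.

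**What to change.** Remove fexofenadine from the oral antihistamine examples in Section 7.5.2.3. Loratadine, cetirizine, diphenhydramine and hydroxyzine remain. None of them is in Appendix 2 or Appendix 3, although Section 7.8.1 warns that absence from those lists does not establish safety with AZD2014.

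Alternatively, if the sponsor's clinicians judge fexofenadine acceptable with AZD2014, add an explicit exemption in Section 7.8.1 and Appendix 3. That would also settle exclusion criterion 4.

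The cost is one deleted word or one added line. The only downside of deletion is one fewer named antihistamine.

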7.5.2.4 Recommendations for Treatment of Hyperglycaemia

Treatment related findings of elevated blood glucose levels should be reported as AE (s) if they fulfil the CTCAE criteria and SAE(s) if meeting the SAE reporting criteria.

In general management of hyperglycaemia should be performed according to local standards at the discretion of the Investigator.Due to the predicted short half-life of AZD2014, only a short period of hyperglycaemia with insulin resistance is expected. Therefore early treatment with high doses of insulin/and or oral anti-diabetes medication should be carefully evaluated and blood sugars and hypokalemia monitored as per standard clinical practice.

If blood glucose levels are < 250 mg/dl (Grade 2), generally no medical treatment is required. Dietary modification may be initiated.

For ≥ Grade 3 hyperglycaemia, dose modifications are required see Section 7.5.1

7.5.2.5 Recommendations for Evaluation and Treatment of Interstitial Lung Disease

Should a patient experience any new respiratory symptoms including cough, dypsnoea, lower respiratory tract infections not clearly explained by other factors such as disease progression or anaemia, a high resolution CT scan should be performed. In addition, pulmonary function tests should be performed. The test should include the highest of 3 forced expiratory volumes (FEV1), forced vital capacity (FVC), and carbon monoxide diffusing capacity (DLCO% & DLCO). A recent haemoglobin measurement should be available at DLCO evaluation.

If these investigations are suggestive of pneumonitis or interstitial lung disease and causality with the study drug cannot be excluded, treatment should be interrupted. In more severe cases treatment with corticosteroids should be considered

7.5.2.6 Recommendations for Evaluation and Management of ECG Changes

Patients who develop persistent, confirmed T wave repolarisation abnormalities (inversion or flattening) on regularly scheduled ECGs may be referred for a cardiology opinion.

ECG monitoring should be continued as per the trial schedule, as well as a troponin measurement (within 24 of the abnormality). ECG, Troponin and LV function assessment should also be conducted at trial discontinuation and 30 days follow-up visit (to document recovery while off drug)

7.5.2.7 Recommendations for Evaluation and Treatment of Severe Fatigue

If \geq Grade 3 fatigue occurs, the dosing should be held for up to 14 days, before being restarted at a lower dose.

Routine clinical work-up to exclude reasons other than the underlying disease and/or AZD2014 treatment may be performed, including laboratory analyses to rule out metabolic (acidosis, hyperglycaemia) or cardiac problems.

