1.2.3.2 Overall Safety of AZD2014

AZD2014 is considered to be generally well tolerated with most of the AEs classified as CTCAE grade 1 and 2. AEs have also been shown to resolve quickly after short periods of dose interruptions, which allowed patients to stay on the drug for long periods of time (over 1 year). Fatigue, mucositis, rash, nausea, vomiting, diarrhoea, hyperglycaemia and decreased appetite, risk of pneumonitis and infections were the AEs consistently amongst the most frequently reported overall, and those reported as related to AZD2014 by the Investigators. These AEs were also those reported with the highest severity grade and were those AEs most commonly leading to dose interruption and/or permanent discontinuation of AZD2014. These events were generally reversible within 1 week by cessation of AZD2014. The AE profile of continuous and intermittent dosing schedules varied slightly. Although gastrointestinal events were observed more frequently in the intermittent schedules, there have been no reports of rash or hyperglycaemia so far for the intermittent dosing schedules.

Overall, no clinically significant changes were observed in heart rate or blood pressure (BP). Single intermittent systolic or diastolic BP values above and below normal values were reported in a few patients. Intermittent higher heart rates >100 bpm were observed, and tachycardia in some patients.

No clinically significant changes were observed in vital signs or laboratory data overall. Review of emerging laboratory data did not reveal clinically significant liver function test (LFT) abnormalities considered related to AZD2014. Transaminase increases (ALT or AST) were reported as AEs in some patients; the majority were CTCAE grade 1 and were not considered related to AZD2014 by the reporting investigator. Laboratory data suggest that for most patients who do have reductions in cell counts, values return to patients' baseline on stopping AZD2014. The clinical relevance of these changes appears low given that there was no excess of related AEs such as infection, fungal disease, viral disease, dyspnoea, or bleeding within these patients when compared with patients not noted as having reductions, and there were no events of greater severity. ECG repolarisation changes were seen in some patients. However, there were no associated significant QRS morphology changes and the clinical significance of these changes is unknown.

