7.5.2.8 Recommendations for Treatment of Diarrhoea

Patients should be made aware of the risk of diarrhoea while receiving treatment with AZD2014. Patients should be advised to drink sufficient fluids and have a supply of loperamide available throughout treatment. However, loperamide should not be administered prophylactically.

As soon as the first liquid stool occurs, patients should start treatment with loperamide immediately and also take electrolyte-containing fluids. Patients should inform their study doctor.

The recommended antidiarrheal treatment is loperamide; to be administered as per package information and usual clinical practice .Loperamide should not be administered for more than 48 consecutive hours.

Hospitalisation is recommended for management of diarrhoea under the following circumstances:

- Diarrhoea associated with fever
- Diarrhoea requiring intravenous hydration
- Diarrhoea persisting beyond 48 hours following the initiation of high-dose loperamide therapy.

Please refer to Section 7.5.1 for dose modifications required for \geq Grade 3 diarrhoea.

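### Section 7.5.2.7 restarts AZD2014 after Grade 3 or worse fatigue without a recovery condition or a pointer to Table 2, whose restart and stopping rules differ; the two passages need reconciling

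*Protocol*

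**What the plan says.** Section 7.5.2.7 of the protocol, one of the specific dose modification sections, states that for fatigue of Grade 3 or worse "the dosing should be held for up to 14 days, before being restarted at a lower dose". Its only other content is an optional work-up for other causes.

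Table 2 in section 7.5.1 covers non-haematological toxicities in general. For Grade 3 or 4 toxicity expected to be manageable with dose reduction, the drug is held and one of two things follows. If the toxicity lasts 14 days or less, the action is "Reduce dose level per Table 1 and restart once toxicity has resolved to grade 2 or less or is no longer clinically significant". The other row reads "Toxicity remains (despite dose interruption) grade 3 or 4 or is clinically significant > 14 days", and its action is to stop the drug. A separate row, "Not expected to be manageable/reversible with dose reduction", also leads to stopping.

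The footnote to Table 2 sets precedence for five topics: "If the below specific recommendations for stomatitis/oral mucositis, hyperglycaemia, ILD/pneumonitis, ECG-changes and rash disagree with table 2 please follow the below" sections rather than the table. Fatigue is not named.

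The diarrhoea section (7.5.2.8), whose topic is also absent from the footnote, sends the reader back: "Please refer to Section 7.5.1 for dose modifications required for" diarrhoea of Grade 3 or worse. The hyperglycaemia section (7.5.2.4) and the Grade 3 rash text (7.5.2.3) likewise refer to section 7.5.1.

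**The concern.** Section 7.5.2.7 gives its own complete-looking instruction to hold and restart. A site treating a patient with severe fatigue would naturally turn to the section with that title and might read no further. Nothing there says that a restart depends on recovery, or that Table 2 applies.

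Fatigue is a foreseeable event. Section 1.2.3.2 lists "Fatigue, mucositis, rash, nausea, vomiting, diarrhoea, hyperglycaemia and decreased appetite" among the most frequently reported adverse events, and says that the events in this group were also those most commonly leading to interruption or permanent discontinuation.

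Two things are at stake. One is patient safety, because a patient could be re-exposed under one passage when the other takes the patient off the drug. The other is consistency: sites following different passages would generate exposure and discontinuation data that reflect the reading chosen as well as the drug.

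**Working it through.** No stated figure bears on this point, so the check is a comparison of the passages, followed by a check of whether the conflict reaches the decision rules.

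**Step 1. The two rules side by side, for Grade 3 or worse fatigue**

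| Situation | Section 7.5.2.7, read literally | Table 2, section 7.5.1 |
|---|---|---|
| Recovered to Grade 2 or less within 14 days | Restart at a lower dose | Restart at a reduced level |
| Still Grade 3 and clinically significant during the hold | No recovery condition on restart | No restart yet |
| Still Grade 3 once the hold has exceeded 14 days | Restart at a lower dose; no stopping branch | Stop the drug |
| Not expected to be manageable by dose reduction | Hold, then restart; no separate branch | Stop the drug |

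The passages agree when fatigue recovers in time. They diverge when it does not, and most clearly at the end of the hold.

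**Step 2. Does the protocol say which passage governs?**

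The footnote's list of five is closed. A toxicity that is not on it falls back on Table 2, so Table 2 governs fatigue by implication. Section 7.5.2.7 does not repeat or acknowledge this.

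**Step 3. Is fatigue treated like the other specific sections?**

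- Diarrhoea: not on the footnote list, but refers to section 7.5.1.
- Hyperglycaemia and rash: on the list, and both refer to section 7.5.1 at Grade 3.
- Stomatitis: on the list, with its own recovery grades and its own 14-day rule.
- Nausea and vomiting, and electrolyte changes: no rule for holding or restarting AZD2014.
- Fatigue: has a rule for holding and restarting, is not on the list, and has no reference to section 7.5.1.

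Among these sections, fatigue is the only one whose hold-and-restart rule is neither given precedence nor tied to Table 2.

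**Step 4. Does the conflict reach the decision rules?**

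- Tolerability (section 12.6): a toxicity counts against the drug if it leads to a treatment delay or dose modification in the first 2 cycles. For the patient in question both routes begin with a hold. If that falls in the first 2 cycles, the patient counts as not tolerating treatment either way. The limits of 10 of 15 and 21 of 30 are met or missed identically.
- Response (section 12.6): the rule of at least 9 responses in 30 patients does not refer to dosing status. Patients who stop without progression continue to have CT, every 3-4 months for a year from first treatment (sections 7.3, note j, and 7.3.4), with a 3-monthly schedule in section 7.10. Stopping the drug therefore does not remove a patient from response assessment.

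**The case against.** The strongest reply is that the protocol already settles the matter. The footnote displaces Table 2 for five toxicities only, so for fatigue Table 2 applies. The two passages can also be read together: hold for at most 14 days, restart at a reduced level on recovery, and otherwise stop. On this reading section 7.5.2.7 is incomplete rather than contradictory, because it is silent on fatigue that persists. A reader might infer that it orders a restart whatever the grade at that time, but those words are not in the text. This reply stands as to which passage governs by implication. It does not remove the need for a correction: the section most likely to be consulted gives an instruction without the condition, and the reader has to find a footnote elsewhere and reason from an omission.

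Three stronger readings are tempting and are not supported.

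- A reader might infer that section 7.5.2.7 leaves patients at the lowest dose level without a rule. Section 7.5 limits reductions to two and allows a case-by-case discussion of continuous dosing. Table 2 covers recurrence of Grade 3 when no further level is available.
- A reader might infer that several of the 30 patients would be affected. The protocol gives no rate of severe fatigue and none of its persistence, and the order of the list in section 1.2.3.2 is not a stated ranking. That section also says that most events were Grade 1 or 2 and that the listed events generally reversed within 1 week of stopping, so persistence beyond 14 days should be uncommon.
- A reader might infer that the conflict could tip the go or no-go decision on response. That would require the restart decision to change a patient's response status, which nothing in the protocol shows. The chance of observing exactly 9 responses is also not the chance that one given patient decides the result.

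**Conclusion.** The point holds as a clarification of conflicting text. Section 7.5.2.7 omits the recovery condition and the stopping branch that Table 2 contains. It is not on the list of sections that override Table 2, and it does not point to section 7.5.1 as comparable sections do. Taken literally, the two passages treat a patient with unresolved Grade 3 fatigue at the end of the hold in opposite ways.

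The consequence lies in patient management and in the consistency of exposure and discontinuation data. The tolerability counts do not change, and neither response nor tolerability decision rules are affected. Lost or added exposure could in principle influence an individual's response, but the protocol offers no basis for putting a size on that. The number of patients involved cannot be derived from the document and is probably small, given its statement on reversibility.

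The conclusion rests on a literal reading of section 7.5.2.7 taken alone. It makes no judgement on which clinical rule is right.

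**What to change.** Reconcile section 7.5.2.7 with Table 2 and state which governs. Either of two edits would do:

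- add a cross-reference from section 7.5.2.7 to section 7.5.1, as the diarrhoea and hyperglycaemia sections have; or
- add fatigue to the toxicities named in the Table 2 footnote. In that case section 7.5.2.7 must itself say what happens to fatigue that has not resolved by the end of the hold, because Table 2 would no longer supply the answer.

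The choice between them is clinical and is for the sponsor's clinicians. The cost is one or two sentences in the next amendment or in a clarification letter to sites. Sample size, endpoints and analysis are unaffected.
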